## Study protocol

This is an ethically approved (clinicaltrial.org NCT03805971) single center cross-sectional study. Every patient  $\geq$  18 years referred for a medical thoracoscopy (pleural effusion work up, recurrent pneumothorax, talc pleurodesis...) was selected for the present study between 06/2018 and 09/2019. Exclusion criteria were pregnancy and known allergy to fluorescein. The thoracoscopy was performed under sedation (allowing spontaneous breathing) by two experienced investigators with a systematic procedure. The patient was positioned in lateral decubitus during the intervention. After chest ultrasound examination, a pneumothorax was induced with the Boutin trocar and one entry port was performed through the chest wall. Two different thoracoscopes were used during this study: Wolf thoracoscope with an outer diameter of 7 mm (Richard Wolf GmbH, Knittlingen Germany ®) and a Storz single puncture thoracoscope with an outer diameter of 10 mm (Karl Storz GmbH, Tuttlingen, Germany ®). Five milliliters of fluorescein (10%) were intravenously administrated 5 minutes before image acquisition. After that, the pleural cavity was examined macroscopically. Then the pCLE probe (Alveoflex ®, lateral resolution 3  $\mu$ m, optical area 1.13 mm^2, depth of focus 0 - 50  $\mu$ m) (Cellvizio®, Maunakea technologies®, Paris, France) was gently placed on the parietal pleura and videos were recorded. If macroscopic abnormalities were noticed, pCLE was performed on affected zones, if not, three random sites were selected. Finally, biopsies were systematically performed on the same sites for comparison with optical biopsies. During the thoracoscopy, the investigators rated the quality of the pCLE acquisitions (good, acceptable, low).

After the image acquisition, another investigator (not included in those who rated the quality of the acquisition) selected the five best representative images for further analysis and comparison to histological samples. According to our previous experience, 11 criteria were selected to assess the ability of pCLE to distinguish benign from malignant pleura. The abnormal tissular architecture was defined by the identification of tissular/cellular structures not known to belong to the normal pleura (cell clusters, dark clumps, glands, cell cordons, dysmorphic cells, papillary architecture...). The absence of abnormal architecture was defined by the identification of normal pleural cellular and tissular elements as previously reported: the mesothelial monolayer with homogenous and regularly distributed cells; the fibro-adipose connective tissue and its regular and homogeneous vascularization; muscular fibers. The cells homogeneity in size, fluorescence and shape was subjectively assessed by the investigator. The mean cellular size was assessed on a full field of view (1.13 mm^2). The presence of dysplastic vessels was assessed, as described by Cannizzaro et al., by the identification of vascular leaks (fluorescein leakage outside the vessels), tortuous vessels or giant vessel. For the maximal vascular diameter, we selected the largest vessels among the available pCLE images. For the vascular density, we measured the max number of vessels/image (full field of view) for every patient on the available images. For our study, we selected only the vessels with a length of at least 50  $\mu$ m. The connective tissue fibers were classified as anarchic or organized. anarchic connective tissue fibers were defined as irregular in shape or direction, coarse, without a well-defined architecture. Organized connective tissue fibers were defined as regular in shape and direction with a well-defined architecture. The chia seed sign defines the presence on a full field of view of the mesothelial monolayer with well defined, homogeneous and organized mesothelial cells. The criteria were not scored if assessable elements for their interpretation were missing. Every patient included gave informed consent.

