## Statistical analysis plan

The Fisher's exact test was used to analyze the link between pCLE qualitative variables and the final histological diagnosis ( $p < 0.05$  for statistical significance). For quantitative variables, the unpaired T-test (2 sided  $p$ -value,  $p < 0.05$ ) was used.

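### Does leaving the coding of 'no mesothelial monolayer seen' unstated distort the Fisher test of the chia seed sign?

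*Combined protocol and SAP*

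**What the plan says.** The Study protocol describes the sign in one sentence: "The chia seed sign defines the presence on a full field of view of the mesothelial monolayer with well defined, homogeneous and organized mesothelial cells". Next comes a rule that applies to all 11 criteria: "The criteria were not scored if assessable elements for their interpretation were missing". What counts as an assessable element is not spelled out for any criterion.

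Two other qualitative criteria have both levels described. For architecture, "The absence of abnormal architecture was defined by the identification of normal pleural cellular and tissular elements". For fibres, "The connective tissue fibers were classified as anarchic or organized". Dysplastic vessels, like the chia seed sign, are described only by what makes them present.

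Scoring rests on a small set of images per patient: an investigator "selected the five best representative images for further analysis and comparison to histological samples". The normal pleura is said to include, besides the monolayer, "the fibro-adipose connective tissue and its regular and homogeneous vascularization; muscular fibers".

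The Statistical analysis plan says only this about qualitative criteria: "The Fisher's exact test was used to analyze the link between pCLE qualitative variables and the final histological diagnosis", with significance at p < 0.05. It states no denominator, no handling of unscored values and no sidedness for Fisher's test.

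**The concern.** A patient whose five images show only fat, muscle or abnormal tissue could be coded in two ways. Under the first, the sign is absent and the patient stays in the table. Under the second, the structure to be judged is missing, so the criterion is not scored and the patient leaves.

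The codings answer different questions. The first asks whether seeing an organised monolayer separates benign from malignant pleura in all patients. The second asks whether its organisation does so among patients whose monolayer was imaged.

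The loss under the second coding is one-sided. A sign-positive patient has the monolayer in view and cannot be dropped for lacking it. The positive cells of the 2×2 table stay fixed and only the negative cells shrink. If the shrinkage differed between benign and malignant patients, and the result were then presented as the sign's performance in everyone, the odds ratio and the p-value could mislead. Images of normal pleura without a monolayer are foreseeable, so the case is not far-fetched.

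**Working it through.** **Inputs.** From the documents: the definition of the sign, the non-scoring rule, and Fisher's exact test at p < 0.05. The documents give no sample size, no sign frequency and no count of unscored patients, so there is no figure of the plan's own to reproduce. Assumed here: a two-sided test, equal groups of 20 or 30, and all category rates below.

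**Step 1: the odds ratio.** Let the odds ratio (OR) compare the odds of the sign in benign with malignant patients. If a share k of the sign-negative patients is kept in each group, then

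scored-only OR = all-patient OR × (k malignant / k benign).

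The odds ratio is unchanged when the two shares are equal, whatever the loss.

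**Step 2: no all-patient association.** Each group is split as organised / disorganised / not seen (%). Malignant is 30/50/20 throughout, so k malignant = 50/70. The sign is present in 30% of both groups, so the all-patient OR is 1.0, and the all-patient test rejects 2.5% (20 per group) or 2.6% (30 per group) of the time. Rejection rates come from exact enumeration of the binomial outcomes, summing over the random number scored in each group.

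| Benign split | Gap in 'not seen' | Scored-only OR | Rejects, 20/20 | Rejects, 30/30 |
|---|---|---|---|---|
| 30/50/20 | 0 points | 50/50 = 1.0 | 2.9% | 3.5% |
| 30/40/30 | 10 points | 50/40 = 1.25 | 3.6% | 4.5% |
| 30/30/40 | 20 points | 50/30 = 1.67 | 6.6% | 9.3% |
| 30/20/50 | 30 points | 50/20 = 2.5 | 14.3% | 21.9% |
| 30/10/60 | 40 points | 50/10 = 5.0 | 31.5% | 49.6% |

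Swapping the groups inverts the odds ratio (5.0 becomes 0.20) at the same rejection rates. These are false positives only for the all-patient question. Wherever the scored-only OR differs from 1, organisation truly differs among imaged monolayers.

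**Step 3: a strong association.** With the sign present in 60% of benign and 10% of malignant patients, the all-patient OR is (60/40)/(10/90) = 13.5, with power 90.8% (20/20) or 98.5% (30/30).

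- Malignant 10/20/70, benign 60/20/20: 13.5 × (20/90)/(20/40) = 6.0; power 33.8% or 51.7%.
- Malignant 10/40/50, benign 60/5/35: 13.5 × (40/90)/(5/40) = 48; power 95.0% or 99.5%.

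The effect can therefore go either way.

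**Step 4: which coding does the text support?** Three comparisons within the Study protocol bear on this.

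1. The sign is defined as a presence: "The chia seed sign defines the presence on a full field of view of the mesothelial monolayer". The ordinary negative of a presence is 'not present'. For such a sign, the assessable element can simply be an interpretable full-field image.
2. The non-scoring rule fits most easily where something must be seen before it can be graded or measured: fibre organisation, cell homogeneity, cell size, vessel diameter.
3. Where absence was meant to require a positive observation, as for abnormal architecture, the text says so. It makes no such demand for the chia seed sign.

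Under this coding nobody leaves the table for want of a monolayer, k = 1 in both groups, and the multiplier in Step 1 is 1.

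**The case for a change.** The strongest case for acting is that the non-scoring sentence directly follows the definition, is general, and makes no exception for this sign. The monolayer is, after all, what one needs in order to judge whether its cells are organised. The one-sided loss follows from the definition and needs no assumed rate. Nothing in the documents suggests that the monolayer would be missed equally often in the two groups. Stating the rule would take one sentence.

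Much of this stands. The coding is indeed unwritten, and the wording does not exclude the second reading. The mechanism is correct for patients removed for this reason; those unscored for other reasons, such as poor images, have unknown status.

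What does not follow is that the plan gives a wrong result. Harm needs three things together: that not-seen patients were left unscored, that the share of negatives kept differed materially by diagnosis, and that the result was presented as performance in all patients. The documents show none of them. A positive-only definition is also not peculiar to this sign, since dysplastic vessels are described the same way. An extra all-patient test would repeat the existing one if not-seen patients were already coded as absent.

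**Conclusion.** The concern does not call for a change. It identifies a missing coding definition for one of 11 criteria, and the natural reading of a presence sign, not seen means absent, fills the gap without losing any patient for this reason. Even the other coding is coherent, provided the result is described as applying to patients whose monolayer was imaged.

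The possible effect ranges from nil to large. In the no-association examples with 30 per group, rejection is 4.5% at a 10-point gap, below the nominal 5%, and reaches 49.6% only at a 40-point gap. Those figures rest wholly on assumed rates, group sizes and a two-sided test, and apply only if not-seen patients were left unscored. The documents cannot settle whether that happened, how often, or in which group. The preference for the natural reading is an inference from the wording, not proof. Giving the number scored for this sign in each diagnosis group when results are presented would be ordinary good reporting; the stated analysis does not need to change for it.

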## Statistical analysis plan

The Fisher's exact test was used to analyze the link between pCLE qualitative variables and the final histological diagnosis ( $p < 0.05$  for statistical significance). For quantitative variables, the unpaired T-test (2 sided  $p$ -value,  $p < 0.05$ ) was used.

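### The plan tests each pCLE criterion for association with histology but plans no estimate, with an interval, of how well it separates benign from malignant pleura

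*Combined protocol and SAP*

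**What the plan says.** No section shown is headed as an aim or objective. The nearest text is in the Study protocol: "11 criteria were selected to assess the ability of pCLE to distinguish benign from malignant pleura". Biopsies were taken at the sites imaged, so each patient has a histological reference.

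The Statistical analysis plan is two sentences long. Fisher's exact test "was used to analyze the link between pCLE qualitative variables and the final histological diagnosis", with p<0.05 "for statistical significance". The second sentence begins "For quantitative variables, the unpaired T-test" and makes that test two-sided at the same level.

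Three further statements in the Study protocol bear on the analysis:

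- An investigator other than those who rated acquisition quality "selected the five best representative images for further analysis and comparison to histological samples".
- Vascular density is reduced to one value per patient: "we measured the max number of vessels/image (full field of view) for every patient on the available images".
- Denominators can differ between criteria: "The criteria were not scored if assessable elements for their interpretation were missing".

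The text available for review mentions no sensitivity, specificity, predictive value, likelihood ratio, ROC curve, cut-off or confidence interval.

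**The concern.** Telling benign from malignant pleura against a biopsy reference is a question of diagnostic accuracy. Its answer is a size with a margin of error: what share of malignant patients the criterion flags, what share of benign patients it clears, and how precisely each is known. A p-value for association answers a narrower question, whether the criterion is related to histology at all.

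Three things are lost if the results are read through p<0.05:

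- The p-value does not show which way a criterion is useful. One that helps to rule malignancy in can have the same p-value as one that helps to rule it out.
- It depends on the number of patients as well as on accuracy.
- It can fall below 0.05 for a criterion that is wrong in a third of patients, or for a measurement whose AUC interval reaches almost to 0.50, the value for no discrimination.

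**Working it through.** **Inputs.** The documents supply the tests (Fisher's exact; unpaired two-sided t) and the 5% level. They give no sample size, group sizes, target accuracy or proportion malignant, so there is no planned figure to reproduce. The group sizes below are assumptions: mainly 30 malignant and 30 benign, with other sizes where stated.

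**Step 1: same p-value, opposite use.** Sensitivity = flagged malignant / all malignant. Specificity = unflagged benign / all benign.

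| Criterion | Sensitivity (exact 95% CI) | Specificity (exact 95% CI) | Fisher p |
|---|---|---|---|
| A | 12/30 = 40% (23-59%) | 27/30 = 90% (73-98%) | 0.0153 |
| B | 27/30 = 90% (73-98%) | 12/30 = 40% (23-59%) | 0.0153 |

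Positive likelihood ratio of A: 0.40/(1 - 0.90) = 4. Negative likelihood ratio of B: (1 - 0.90)/0.40 = 0.25. A is informative when present and B when absent. The planned test returns one number for both.

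**Step 2: how modest a significant criterion can be.** With 20/30 correct in each group, sensitivity = specificity = 67% (exact 95% CI 47-83%), and Fisher p=0.019. One fewer correct in each group (19/30) gives p=0.070. So a criterion that misclassifies 10/30 = 33% of each group passes p<0.05. This is one case among many: 15/30 = 50% sensitivity (31-69%) with 24/30 = 80% specificity (61-92%) also passes, at p=0.029.

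**Step 3: same accuracy, different p-value.** Hold sensitivity = specificity = 70%:

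| Per group | Correct in each group | Fisher p |
|---|---|---|
| 10 | 7/10 | 0.18 |
| 20 | 14/20 | 0.026 |
| 30 | 21/30 | 0.004 |
| 50 | 35/50 | 0.0001 |

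**Step 4: the t-test.** With n per group, a result exactly at two-sided p=0.05 has standardised difference d = t(0.975; 2n - 2) × √(2/n). Under normal distributions with equal variance, AUC = Φ(d/√2). For n = 30:

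- d = 2.002 × √(2/30) = 0.517
- AUC = Φ(0.517/1.414) = Φ(0.365) = 0.643
- Hanley-McNeil standard error = 0.071, so the 95% CI is 0.643 ± 1.96 × 0.071, or about 0.50 to 0.78

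The same calculation gives d = 0.640 and AUC 0.67 (0.51-0.84) for n = 20, and d = 0.397 and AUC 0.61 (0.50-0.72) for n = 50.

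**The case against.** The strongest reply is that the missing quantities can be recovered. Sensitivity and specificity are row proportions of the very 2x2 tables that Fisher's test uses. Step 4 above itself turns a t-test into an AUC. A reader might infer that discrimination cannot be recovered for the quantitative criteria, and that goes too far: a reported t value or exact p-value with group sizes gives an approximate AUC, though only under the normal, equal-variance model. What stands is that the plan commits neither to reporting the counts nor to any estimate or interval, so delivery depends on what happens to be reported.

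The reply also has force on these points:

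- Testing one criterion at a time is a legitimate first step. The plan does not say that conclusions will rest on p<0.05 alone, so the harm is conditional on the results being read that way.
- The link to an aim is an inference from the sentence explaining why the criteria were chosen.
- Which criteria are quantitative is also inferred, because the Study protocol describes mean cell size, maximal vascular diameter and vascular density without classifying the 11 criteria.
- A reader might infer that the unit of analysis and the two-way split of histology are undefined. The Study protocol largely answers both: it takes vascular density per patient and names the benign/malignant contrast.
- Intervals computed on the five best images could suggest more certainty than that selection allows, and the text does not say whether the selector knew the histology. This argues for stating the limit beside the estimates.

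**Conclusion.** The point holds in a limited form. The planned tests are valid for association. Followed as written, they give no estimate or interval for the ability that the criteria were chosen to assess.

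The size can only be illustrated, because all group sizes are assumed. With 30 per group, p<0.05 is compatible with a third of each group misclassified, or with an AUC of about 0.64 whose interval starts at about 0.50. A reader might take 67%, or the matching value at another size, as the accuracy at which significance begins. It is not a general threshold: it applies only to equal groups with sensitivity equal to specificity, and Step 2 shows another pair that also passes. The AUC figures rest further on equal-variance normality.

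The documents do not support a claim that the tests are wrong, or that any particular criterion has been misjudged. The gap is worth closing because the remedy uses data already collected.

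**What to change.** Add an accuracy analysis to the Statistical analysis plan, with the patient as the unit and final histology classed as benign or malignant.

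- **Qualitative criteria:** for each, give the 2x2 counts and the sensitivity and specificity with Clopper-Pearson 95% CIs. State which category counts as malignant.
- **Criteria that appear quantitative** (mean cell size, maximal vascular diameter, vascular density): give the ROC AUC with its 95% CI.
- **Denominators:** give the number scored for each criterion by histological group.
- **Interpretation:** base statements about discrimination on these estimates and keep the Fisher and t-test p-values as supportive. State that the estimates apply to the five selected images.
- **Status:** inclusion ran from 06/2018 to 09/2019, so label as post hoc any of these analyses added after data collection. Rewording the plan now would not make them prespecified.

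The cost is a few lines of analysis and wording, with no new patients or procedures. The downside is that some criteria will look less favourable once their intervals are shown.
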